6.3 Adjustments for Multiple Objectives

An overall significance level of 0.05 ($\alpha = 0.05$) is used.

This study has two sets of objectives, one for Health Canada (HC) analysis and the other for US FDA analysis. These two sets of objectives are considered independently of each other and no multiplicity adjustment between two sets of objectives is performed.

Within the HC analysis primary objectives, since the study HC efficacy analysis will declare success when and only when all four primary objectives pass HC analysis acceptance criteria, no multiplicity adjustment is required [3].

Within the FDA efficacy analysis, a gatekeeping procedure will be applied: the efficacy analysis for two secondary objectives [30-second (abdomen only) post-product application time point] will be performed only when all four primary objectives [10-minute (abdomen and groin) post-product application time point] pass the acceptance criteria. No multiplicity adjustment between primary and secondary objectives is performed. For primary objectives [10-minute (abdomen and groin) post-product application time point], since it will declare success when and only when all four primary objectives pass FDA analysis acceptance criteria, no multiplicity adjustment for the four primary objectives is required [3]. For secondary objectives [30-second (abdomen only) post-product application time point], since it will declare success when and only when all four primary and two secondary objectives pass FDA analysis acceptance criteria, no multiplicity adjustment for the two secondary objectives is required [3].

6.4 Handling of Missing Data and Sensitivity Analysis

Missing \log_{10} CFU/cm² determinations at 30 seconds, 10 minutes, or 6 hours, such as due to laboratory error or subject lost to follow up, will be reported as missing and will not be imputed for main analyses (log reduction, ATE and responder rate) as described in Section 6.2. Missing product weight will be also reported as missing and will not be imputed. Details of any missing data and rationale for inclusion/exclusion in the mITT or PP data set will be described in the statistical or study report.

Sensitivity analysis will be performed to evaluate the impact of missing data, if any, for primary and secondary objectives (refer to Section 6.4.1 for details).

- For HC analysis (log reduction), if acceptance criteria are met for primary objectives, sensitivity analysis will be performed for primary objectives based on the mITT population sets. No sensitivity analysis will be performed if acceptance criteria are not met for primary objectives.
- For FDA analysis (ATE), if acceptance criteria are met for both primary and secondary objectives, sensitivity analysis will be performed separately for primary and secondary objectives based on the mITT population sets. If acceptance criteria are met for primary objectives but not for secondary objectives, sensitivity analysis will be only performed for primary objectives based on the mITT population sets and no sensitivity analysis will be performed for secondary objectives. No sensitivity analysis will be performed if acceptance criteria are not met for primary objectives.
- No sensitivity analysis will be performed for exploratory objectives.

6.4.1 Sensitivity Analysis

For \log_{10} CFU/cm² determinations, multiple imputation under the assumption that data are missing at random (MAR) will be performed to impute a series of \log_{10} CFU values relative to the baseline \log_{10} CFU values for all missing data points.

- For HC objectives, the multiple imputation will be performed separately for each of the four primary objectives (IP only).
- For FDA objectives, the multiple imputation will be performed separately for each of the four primary and two secondary objectives.

If results based on imputed data meet the acceptance criteria, a tipping-point sensitivity analysis will be performed by shifting the imputed values to assess how severe departures from missing at random (MAR) must be in order to find the tipping point at which the acceptance criteria would not be met.

Multiple imputation and tipping point approaches for either HC objectives or FDA objectives include the following steps:

1. The missing data are filled in 25 times to generate 25 complete data sets using Predictive Mean Matching (PPM) method provided in R package “MICE”.
2. Each of the 25 complete data sets are analyzed by using routine analysis method applied for log reduction analysis (HC objectives) or for ATE analysis (FDA objectives).
3. The results from the 25 complete data sets are combined/pooled for the inference and compared to the acceptance criteria (cf. Tables [A.5.1](#) for HC objectives and [A.5.2](#) for FDA objectives).
4. If results based on imputed data meet the acceptance criteria, repeat Step 1 to generate multiple imputed data sets, with a specified shift parameter that shifts the imputed values (shift parameter will be applied to the IP group only).
 - For log reduction, the shift parameter will start from -0.1 to smaller (more stringent) numbers (i.e., -0.1, -0.2, ...).
 - For ATE of IP-AC or NC-IP, the shift parameter will start from 0.1 to larger (more stringent) numbers (i.e., 0.1, 0.2, ...);
5. Repeat Step 2 for the imputed data sets with shift parameter applied.
6. Repeat Step 3 to obtain the estimate and 95% confidence limits to see if acceptance criteria are met.
7. Repeat Steps 4-6 with more stringent shift parameters applied until acceptance criteria are not met.

The tipping point for the shift parameter that reverses the conclusion (“Met Criteria” changes from “Yes” to “No”) will be listed (cf. Tables [A.5.3](#) for HC objectives and [A.5.4](#) for FDA objectives).

For responder rate at 6 hours (FDA objectives), subjects with missing \log_{10} CFU/cm² determinations at 6 hours will not be excluded from sensitivity analysis. Missing data will be imputed by increasing the assumed number of failures sequentially from 0/M to M/M, where M is the number of missing data points at 6 hours. This sensitivity analysis will be performed for all products (IP, AC and NC) on each anatomical site and will provide information on the possible effect of missing data on study results (cf. Table [A.5.5](#)).

6.5 Demographics/Other Descriptive Information

Demographics: Table [A.6.1](#) shows demographics information for subjects in ITT population sets.

Procedure Overview: Any sampling fluid from sampling site that extended to other remaining sites at a certain time point will be listed for each body location (cf. Listing [B.8](#)). Any dressing application that was placed on the application site at the 10-minute time point and dressing integrity was compromised any time prior to the 6-hour time point will be listed for each body location (cf. Listing [B.9](#)). This will be based on data from ITT population sets.

Core Lab Overview: Any sampling solution that was lost at any time during the procedure will be listed with time points affected (cf. Listing [B.10](#)). This will be based on data from ITT population sets.

Product Failures/Lab Accidents/User Errors: Any product failures/lab accidents/user errors will be listed for all study products used (cf. Listing [B.11](#)).

7 References

- [1] ASTM E1173-15. *Standard Test Method for Evaluation of Preoperative, Precatheterization, or Preinjection Skin Preparations*. ASTM International, West Conshohocken, PA, 2015.
- [2] R Core Team. *R: A Language and Environment for Statistical Computing*. R Foundation for Statistical Computing, Vienna, Austria, 2016. URL <https://www.R-project.org/>.
- [3] Frank Bretz, Alex Dmitrienko, Ajit C. Tamhane. *Multiple Testing Problems in Pharmaceutical Statistics*. Chapman and Hall/CRC, 2009.

8 Appendix

A Tables

A.1 Analysis Population Set(s)

Table A.1.1: Overall Subject Disposition

Subject Information	Number of Subjects	Comments
Subjects Screened	n	
Subjects who Passed I/E Criteria	n	
Subjects Enrolled	n	
Subjects Randomized	n	
Subjects Randomized and Treated (ITT)	n	
Subjects who Completed the Study	n	

Table A.1.2: Number of Evaluable Subjects for HC Analysis

Body Location	Population Sets	IP	RS	Overall
Abdomen/Groin	ITT Safety	n	n	n
	mITT CFU Count 30 Seconds	n	n	n
	PP CFU Count 30 Seconds	n	n	n
	mITT CFU Count 10 Minutes	n	n	n
	PP CFU Count 10 Minutes	n	n	n
	mITT CFU Count 6 Hours	n	n	n
	PP CFU Count 6 Hours	n	n	n
	mITT Product Weight	n	n	n
	PP Product Weight	n	n	n

Table A.1.3: Number of Evaluable Subjects for FDA Analysis

Body Location	Population Sets	IP	AC	NC	Overall
Abdomen/Groin	ITT Safety	n	n	n	n
	mITT CFU Count 30 Seconds	n	n	n	n
	PP CFU Count 30 Seconds	n	n	n	n
	mITT CFU Count 10 Minutes	n	n	n	n
	PP CFU Count 10 Minutes	n	n	n	n
	mITT Responder Rate 6 Hours	n	n	n	n
	PP Responder Rate 6 Hours	n	n	n	n
	mITT Product Weight	n	n	n	n
	PP Product Weight	n	n	n	n

A.2 HC Analysis

Table A.2.1: mITT/PP - Summary Statistics for HC Analysis - Log CFU

Body Location	Product	Time Point	Count	Mean	Median	SD	Range (Min-Max)
Abdomen/Groin	IP/RS	Baseline	n	x.xx	x.xx	x.xx	x.xx - x.xx
		30 Seconds	n	x.xx	x.xx	x.xx	x.xx - x.xx
		10 Minutes	n	x.xx	x.xx	x.xx	x.xx - x.xx
		6 Hours	n	x.xx	x.xx	x.xx	x.xx - x.xx

Table A.2.2: mITT/PP - Summary Statistics for HC Analysis - Log Reduction

Body Location	Product	Time Point	Count	Mean	Median	SD	Range (Min-Max)
Abdomen/Groin	IP/RS	30 Seconds	n	x.xx	x.xx	x.xx	x.xx - x.xx
		10 Minutes	n	x.xx	x.xx	x.xx	x.xx - x.xx
		6 Hours	n	x.xx	x.xx	x.xx	x.xx - x.xx

Table A.2.3: mITT/PP - Summary Statistics for HC Analysis - Product Weight

Body Location	Product	Count	Mean	Median	SD	Range (Min-Max)
Abdomen/Groin	IP/RS	n	x.xx	x.xx	x.xx	x.xx - x.xx

Table A.2.4: mITT/PP - Analysis Results for HC Analysis - Log Reduction at 30 Seconds and 6 Hours

Body Location	Product	Time Point	Count	Mean Log Reduction (95% CI)	Met Criteria
Abdomen/Groin	IP/RS	30 Seconds	n	x.xx (x.xx, x.xx)	Yes/No
		6 Hours	n	x.xx (x.xx, x.xx)	Yes/No

Table A.2.5: mITT/PP - Analysis Results for for HC Analysis - Log Reduction at 10 Minutes

Body Location	Product	Time Point	Count	Mean Log Reduction (95% CI)
Abdomen/Groin	IP/RS	10 Minutes	n	x.xx (x.xx, x.xx)

Table A.2.6: mITT/PP - Analysis Results for for HC Analysis - Difference in Log Reduction

Body Location	Contrast	Time Point	Difference in Log Reduction (95% CI)	Conclusion
Abdomen/Groin	IP-RS	30 Seconds	x.xx (x.xx, x.xx)	Sign. Diff/No Sign. Diff
Abdomen/Groin	IP-RS	10 Minutes	x.xx (x.xx, x.xx)	Sign. Diff/No Sign. Diff
Abdomen/Groin	IP-RS	6 Hours	x.xx (x.xx, x.xx)	Sign. Diff/No Sign. Diff

A.3 FDA Analysis

Table A.3.1: mITT/PP - Summary Statistics for FDA Analysis - Log CFU

Body Location	Product	Time Point	Count	Mean	Median	SD	Range (Min-Max)
Abdomen/Groin	IP/AC/NC	Baseline	n	x.xx	x.xx	x.xx	x.xx - x.xx
		30 Seconds	n	x.xx	x.xx	x.xx	x.xx - x.xx
		10 Minutes	n	x.xx	x.xx	x.xx	x.xx - x.xx
		6 Hours	n	x.xx	x.xx	x.xx	x.xx - x.xx

Table A.3.2: mITT/PP - Summary Statistics for FDA Analysis - Log Reduction

Body Location	Product	Time Point	Count	Mean	Median	SD	Range (Min-Max)
Abdomen/Groin	IP/AC/NC	30 Seconds	n	x.xx	x.xx	x.xx	x.xx - x.xx
		10 Minutes	n	x.xx	x.xx	x.xx	x.xx - x.xx
		6 Hours	n	x.xx	x.xx	x.xx	x.xx - x.xx

Table A.3.3: mITT/PP - Summary Statistics for FDA Analysis - Responder Rate at 6 Hours

Body Location	Product	Responder Rate
Abdomen/Groin	IP/AC/NC	n/N (%)

Note: n is number of responders and N is total number of evaluable subjects.

Table A.3.4: mITT/PP - Summary Statistics for FDA Analysis - Product Weight

Body Location	Product	Count	Mean	Median	SD	Range (Min-Max)
Abdomen/Groin	IP/AC/NC	n	x.xx	x.xx	x.xx	x.xx - x.xx

Table A.3.5: mITT/PP - Analysis Results for FDA Analysis - ATE at 10 Minutes

Body Location	Contrast	Time Point	ATE (95% CI)	Met Criteria
Abdomen/Groin	IP-AC	10 Minutes	x.xx (x.xx, x.xx)	Yes/No
Abdomen/Groin	NC-IP	10 Minutes	x.xx (x.xx, x.xx)	Yes/No

Table A.3.6: mITT/PP - Analysis Results for for FDA Analysis - ATE at 30 Seconds

Body Location	Contrast	Time Point	ATE (95% CI)	Met Criteria
Abdomen	IP-AC	30 Seconds	x.xx (x.xx, x.xx)	Yes/No
Abdomen	NC-IP	30 Seconds	x.xx (x.xx, x.xx)	Yes/No

A.4 Safety Analysis

Table A.4.1: ITT - Summary Statistics for Irritation Scores for Abdomen/Groin at Baseline/30 Seconds/10 Minutes/6 Hours

Characteristic	IP	RS	AC	NC	Overall
Erythema					
0-No reaction	n (%)	n (%)	n (%)	n (%)	n (%)
1-Mild and/or transient redness	n (%)	n (%)	n (%)	n (%)	n (%)
2-Moderate redness	n (%)	n (%)	n (%)	n (%)	n (%)
3-Severe redness	n (%)	n (%)	n (%)	n (%)	n (%)
Edema					
0-No reaction	n (%)	n (%)	n (%)	n (%)	n (%)
1-Mild and/or transient swelling	n (%)	n (%)	n (%)	n (%)	n (%)
2-Moderate swelling	n (%)	n (%)	n (%)	n (%)	n (%)
3-Severe swelling	n (%)	n (%)	n (%)	n (%)	n (%)
Rash					
0-No reaction	n (%)	n (%)	n (%)	n (%)	n (%)
1-Mild and/or transient rash	n (%)	n (%)	n (%)	n (%)	n (%)
2-Moderate rash	n (%)	n (%)	n (%)	n (%)	n (%)
3-Severe rash	n (%)	n (%)	n (%)	n (%)	n (%)
Dryness					
0-No reaction	n (%)	n (%)	n (%)	n (%)	n (%)
1-Mild and/or transient dryness	n (%)	n (%)	n (%)	n (%)	n (%)
2-Moderate dryness	n (%)	n (%)	n (%)	n (%)	n (%)
3-Severe dryness	n (%)	n (%)	n (%)	n (%)	n (%)

Table A.4.2: ITT - Adverse Events Summary

Characteristic	IP	RS	AC	NC	Overall
Adverse Events					
No	n (%)	n (%)	n (%)	n (%)	n (%)
Yes	n (%)	n (%)	n (%)	n (%)	n (%)

Note: Overall column is calculated based on overall unique subjects included in ITT.

Table A.4.3: ITT - Safety Analysis - Overall Comparisons for Erythema/Edema/Rash/Dryness

Body Location	Time Point	p-value	Conclusion
Abdomen/Groin	30 Seconds	0.xxx	Sign. Diff/No Sign. Diff
Abdomen/Groin	10 Minutes	0.xxx	Sign. Diff/No Sign. Diff
Abdomen/Groin	6 Hours	0.xxx	Sign. Diff/No Sign. Diff

Note: If analysis is not applicable, p-value will be shown as “N/A”.

Table A.4.4: ITT - Safety Analysis - Subgroup Comparisons for Irritation Scores

Body Location	Characteristic	Time Point	Comparison	Odds Ratio (95% CI)	Conclusion
Abdomen/Groin				x.xx (x.xx, x.xx)	Sign. Diff/No Sign. Diff

A.5 Sensitivity Analysis

Table A.5.1: Pooled Analysis Results Based on Imputed Datasets for HC Objectives - Log Reduction

Body Location	Product	Time Point	Log Reduction (95% CI)	Met Criteria
Abdomen/Groin	IP	30 Seconds	x.xx (x.xx, x.xx)	Yes/No
	IP	6 Hours	x.xx (x.xx, x.xx)	Yes/No

Table A.5.2: Pooled Analysis Results Based on Imputed Datasets for FDA Objectives - ATE

Body Location	Time Point	Contrast	ATE (95% CI)	Met Criteria
Abdomen/Groin	10 Minutes	IP-AC	x.xx (x.xx, x.xx)	Yes/No
	10 Minutes	NC-IP	x.xx (x.xx, x.xx)	Yes/No
Abdomen	30 Seconds	IP-AC	x.xx (x.xx, x.xx)	Yes/No
	30 Seconds	NC-IP	x.xx (x.xx, x.xx)	Yes/No

Table A.5.3: Tipping Point Analysis for HC Objectives - Log Reduction

Body Location	Product	Time Point	Shift Parameter	Log Reduction (95% CI)	Met Criteria
Abdomen/Groin	IP	30 Seconds	-x.x	x.xx (x.xx, x.xx)	Yes
	IP	30 Seconds	-x.x	x.xx (x.xx, x.xx)	Yes
	IP	30 Seconds	-x.x	x.xx (x.xx, x.xx)	No
	IP	6 Hours	-x.x	x.xx (x.xx, x.xx)	Yes
	IP	6 Hours	-x.x	x.xx (x.xx, x.xx)	Yes
	IP	6 Hours	-x.x	x.xx (x.xx, x.xx)	No

Table A.5.4: Tipping Point Analysis for FDA Objectives - ATE

Body Location	Time Point	Contrast	Shift Parameter	ATE (95% CI)	Met Criteria
Abdomen/Groin	10 Minutes	IP-AC	x.x	x.xx (x.xx, x.xx)	Yes
	10 Minutes	IP-AC	x.x	x.xx (x.xx, x.xx)	Yes
	10 Minutes	IP-AC	x.x	x.xx (x.xx, x.xx)	No
	10 Minutes	NC-IP	x.x	x.xx (x.xx, x.xx)	Yes
	10 Minutes	NC-IP	x.x	x.xx (x.xx, x.xx)	Yes
	10 Minutes	NC-IP	x.x	x.xx (x.xx, x.xx)	No
Abdomen	30 Seconds	IP-AC	x.x	x.xx (x.xx, x.xx)	Yes
	30 Seconds	IP-AC	x.x	x.xx (x.xx, x.xx)	Yes
	30 Seconds	IP-AC	x.x	x.xx (x.xx, x.xx)	No
	30 Seconds	NC-IP	x.x	x.xx (x.xx, x.xx)	Yes
	30 Seconds	NC-IP	x.x	x.xx (x.xx, x.xx)	Yes
	30 Seconds	NC-IP	x.x	x.xx (x.xx, x.xx)	No

Table A.5.5: Sensitivity Analysis for FDA Objectives - Responder Rate at 6 Hours

Body Location	Product	Subjects Imputed to Non-responders	Responder Rate
Abdomen/Groin	IP/AC/NC	+0	n/N (%)
		+1	n/N (%)
		+2	n/N (%)
		...	n/N (%)
		+M	n/N (%)

Note: Subjects imputed to non-responders are added to the denominator (N) for the responder rate.

A.6 Demographics

Table A.6.1: ITT - Demographics

Characteristic	IP	RS	AC	NC	Overall
Age at Time of Informed Consent (Years)					
Mean	x.x	x.x	x.x	x.x	x.x
Median	x.x	x.x	x.x	x.x	x.x
SD	x.x	x.x	x.x	x.x	x.x
Min, Max	x.x	x.x	x.x	x.x	x.x
Total Count	n	n	n	n	n
Gender					
Male	n (%)	n (%)	n (%)	n (%)	n (%)
Female	n (%)	n (%)	n (%)	n (%)	n (%)
Ethnicity					
Hispanic or Latino	n (%)	n (%)	n (%)	n (%)	n (%)
Not Hispanic or Latino	n (%)	n (%)	n (%)	n (%)	n (%)
Race					
American Indian or Alaska Native	n (%)	n (%)	n (%)	n (%)	n (%)
Asian	n (%)	n (%)	n (%)	n (%)	n (%)
Black or African American	n (%)	n (%)	n (%)	n (%)	n (%)
Native Hawaiian or Other Pacific Islander	n (%)	n (%)	n (%)	n (%)	n (%)
White	n (%)	n (%)	n (%)	n (%)	n (%)
Other	n (%)	n (%)	n (%)	n (%)	n (%)

Note: Overall column is calculated based on overall unique subjects included in ITT.

B Listings

Table B.1: Protocol Deviations

RandID	Nature of Deviation	Additional Details
Rxxxx		
Rxxxx		
Rxxxx		
Rxxxx		

Table B.2: Subjects with Excluded Data for HC Analysis

RandID	Body Location	Product	Time Point	Included in mITT CFU Count	Included in PP CFU Count
Rxxxx				Yes/No	Yes/No
Rxxxx				Yes/No	Yes/No
Rxxxx				Yes/No	Yes/No
Rxxxx				Yes/No	Yes/No

Table B.3: Subjects with Excluded Data for FDA Analysis

RandID	Body Location	Product	Time Point	Included in mITT CFU Count	Included in PP CFU Count	Included in mITT Responder Rate	Included in PP Responder Rate	Included in mITT Product Weight	Included in PP Product Weight
Rxxxx				Yes/No	Yes/No	Yes/No	Yes/No	Yes/No	Yes/No
Rxxxx				Yes/No	Yes/No	Yes/No	Yes/No	Yes/No	Yes/No
Rxxxx				Yes/No	Yes/No	Yes/No	Yes/No	Yes/No	Yes/No
Rxxxx				Yes/No	Yes/No	Yes/No	Yes/No	Yes/No	Yes/No

Table B.4: Subjects who Did Not Complete the Study

RandID	Subject's Status	Comments
Rxxxx	Screen Failure	
Rxxxx		
Rxxxx		
Rxxxx		

Table B.5: Subjects Not Passing Treatment-day Baseline Criteria

RandID	Body Location	Product	Time Point	Result (log ₁₀)
Rxxxx				x.xx
Rxxxx				x.xx
Rxxxx				x.xx
Rxxxx				x.xx

Table B.6: Adverse Events

RandID	AE Term	Start Date	End Date	AE Outcome	Severity	Relationship to Device	Relationship to Procedure	SAE	Additional Details	Included in ITT
Rxxxx								Yes/No		Yes/No
Rxxxx								Yes/No		Yes/No
Rxxxx								Yes/No		Yes/No
Rxxxx								Yes/No		Yes/No

Table B.7: Serious Adverse Events

RandID	AE Term	Start Date	End Date	Serious Criteria	Hospital Admission Date	Hospital Discharge Date	Was SAE Unexpected/Unanticipated	Included in ITT
Rxxxx							Yes/No	Yes/No
Rxxxx							Yes/No	Yes/No
Rxxxx							Yes/No	Yes/No
Rxxxx							Yes/No	Yes/No

Table B.8: Procedure Overview - Sampling Fluid

RandID	Body Location	Product	Did Sampling Fluid from Sampling Site Extend to Other Remaining Sites at Any Time Point	Time Points Affected
Rxxxx			Yes	30 Seconds
Rxxxx			Yes	
Rxxxx			Yes	
Rxxxx			Yes	

Table B.9: Procedure Overview - Dressing Application

RandID	Body Location	Product	Was Dressing Application Placed on the Application Site at the 10 Minute Time Point	Was Dressing Integrity Compromised at Any Time Prior to the 6 Hour Time Point	Details
Rxxxx			Yes	Yes	Subject Confirmed Dressing was Adjusted and/or Touched
Rxxxx			Yes	Yes	
Rxxxx			Yes	Yes	
Rxxxx			Yes	Yes	

Table B.10: Core Lab Procedure Overview - Sample Solution

RandID	Body Location	Product	Was Any Sampling Solution Lost at Any Time During the Procedure	Time Point Affected	Volume Remaining (mL)
Rxxxx			Yes	Baseline	
Rxxxx			Yes		
Rxxxx			Yes		
Rxxxx			Yes		

Table B.11: Product Failures/Lab Accidents/User Errors

RandID	Are There Any Product Failures/Lab Accidents/User Errors to Report	Date of Incident	Product Affected	Time of Incident	Incident Code	Details	Was Product Used on Study Subject	Was an AE Associated with the Incident
Rxxxx	Yes			During Product Exposure	Product Handling Issue			
Rxxxx	Yes							
Rxxxx	Yes							
Rxxxx	Yes							

C Figures

C.1 HC Analysis

[figure not shown]

Figure C.1.1: mITT/PP - Log Reduction with 95% CI (Example Data Only)

C.2 FDA Analysis

[figure not shown]

Figure C.2.1: mITT/PP - ATE with 95% CI (Example Data Only)

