13.4 Handling of Missing Data

Missing \log_{10} CFU/ cm^2 determinations at 30 seconds, 10 minutes, or 6 hours, such as due to laboratory error or subject lost to follow up, will be reported as missing and will not be imputed. Inclusion of these subjects in the per-protocol data set will be based on the criteria defined above and within the SAP. Details of any missing data and rationale for inclusion/exclusion in the per-protocol data set will be described in the study report.

For FDA analysis objectives: For \log_{10} CFU/ cm^2 determinations, a tipping-point sensitivity analysis will use multiple imputation to impute a series of \log_{10} CFU values relative to the baseline \log_{10} CFU values for all missing data points in order to find the point at which the objectives at 30 seconds and 10 minutes would not be met. The multiple imputation will be performed separately for each of the 4 primary and 2 secondary comparisons.

For responder rate calculations from 6-hour data (FDA analysis), subjects with missing \log_{10} CFU/ cm^2 determinations at 6 hours will not be excluded from analysis. Missing data will be imputed by increasing the assumed number of failures sequentially from 0/M to M/M, where M is the number of missing data points at 6 hours. This sensitivity analysis will be performed for all products on each anatomical site and will provide information on the possible effect of missing data on study results.

Detailed description of sensitivity analysis performed will be described in the statistical analysis plan.

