2.5 Acceptance Criteria

To be included in the primary analysis [modified intent-to-treat (mITT) data set], a product application site must have a Product Application Day microbial baseline within the stated requirements. Table 1 summarizes the baseline criteria for the mITT data set for each anatomical site and the expected minimum efficacy country specific standards.

For HC primary objectives, it will declare success when and only when all four primary objectives pass HC analysis acceptance criteria.

For FDA primary objectives [10-minute (abdomen and groin) post-product application time point], it will declare success when and only when all four primary objectives pass FDA analysis acceptance criteria. For FDA secondary objectives [30-second (abdomen only) post-product application time point], a gatekeeping procedure will be applied: the efficacy analysis for two secondary objectives will be performed only when all four primary objectives [10-minute (abdomen and groin) post-product application time point] pass the acceptance criteria and it will declare success when and only when all four primary and two secondary objectives pass FDA analysis acceptance criteria.

For responder rate at 6 hours, no acceptance criteria are applied.

Table 1: mITT Data Set for Each Anatomical Site and Expected Minimum Efficacy Standards

Anatomical Product Application Site	Product Application Day Baseline Criteria	HC Analysis Acceptance Criteria at 30 Seconds, Primary Objectives	HC Analysis Acceptance Criteria at 6 Hours, Primary Objectives	FDA Analysis Acceptance Criteria at 30 Seconds, Secondary Objectives	FDA Analysis Acceptance Criteria at 10 Minutes, Primary Objectives
Abdomen	3.20 to 6.00 \log_{10} CFU/cm ²	Immediate effectiveness for the IP is at least a 2- \log_{10} CFU/cm ² reduction from baseline skin flora counts at 30 seconds.	Persistence effectiveness for the IP is at least a 2- \log_{10} CFU/cm ² reduction from baseline skin flora counts at 6 hours.	At 30 seconds the upper two-sided 95% confidence bound of the average treatment effect (ATE) of IP - AC should be less than 0.5 \log_{10} . At 30 seconds the lower two-sided 95% confidence bound of the ATE of NC - IP should be greater than 1.2 \log_{10} .	At 10 minutes the upper two-sided 95% confidence bound of the average treatment effect (ATE) of IP - AC should be less than 0.5 \log_{10} . At 10 minutes the lower two-sided 95% confidence bound of the ATE of NC - IP should be greater than 1.2 \log_{10} .

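### The note to SAP Table A.5.5 leaves out missing 6-hour sites that SAP 6.4.1 and Protocol 13.4 keep, so the best-case row is not shown (minor, and only if counts are missing)

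*SAP*

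**What the plan says.** Protocol 13.4 states that subjects with missing "determinations at 6 hours will not be excluded from analysis". SAP 6.4.1 repeats this for the responder rate, in that such subjects "will not be excluded from sensitivity analysis". Both documents give the same scheme: "Missing data will be imputed by increasing the assumed number of failures sequentially from 0/M to M/M", with M the number of missing 6-hour data points. SAP 6.4.1 adds that the exercise covers IP, AC and NC on each anatomical site and "will provide information on the possible effect of missing data on study results".

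The shell that implements this is SAP Table A.5.5, with rows +0, +1, +2 up to +M. Its note reads: "Subjects imputed to non-responders are added to the denominator (N) for the responder rate".

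The main responder-rate table, SAP Table A.3.3, defines its terms: "n is number of responders and N is total number of evaluable subjects". SAP 6.4 leaves missing counts unimputed in the main responder-rate analysis, so that N does not contain the M missing sites.

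On the weight of the result, SAP 2.5 says: "For responder rate at 6 hours, no acceptance criteria are applied". SAP 6.2.2.1 rules out inferential analysis of the rate.

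**The concern.** The text and the table note lead to different calculations. If all M missing sites stay in the analysis and k of them are assumed to fail, the other M−k have to be counted as responders, and the denominator is N+M in every row. The note puts only the imputed non-responders into the denominator. The remaining M−k sites then appear in neither numerator nor denominator, which is exclusion in all but name.

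What is at stake is the table's own purpose. It is meant to show how far missing data could move the rate. Built from the note, it shows movement downward from the complete-case rate and none upward.

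**Working it through.** **Inputs.** n = observed responders and N = evaluable sites (Table A.3.3); M = sites with a missing 6-hour count; k = number imputed as failures, 0 to M (SAP 6.4.1, Table A.5.5). The documents state no value for n, N or M at 6 hours and no responder rate, so there is no figure of the plan's to reproduce. For scale, the examples use N+M = 280, the minimum number of evaluable sites per product and body location in Protocol 4.0. M and the rates are assumed.

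**Formulas.**

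- Note: rate at row +k = n/(N+k).
- Text: rate at row +k = (n+M−k)/(N+M).
- Text minus note = [(n+M−k)(N+k) − n(N+M)] / [(N+M)(N+k)] = (M−k)(N+k−n) / [(N+M)(N+k)].

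The difference is never negative. It is zero at k = M, and at k = 0 when every observed site responds (n = N). Otherwise the note's rate is the lower one.

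**Span from row +0 to row +M.**

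- Text: (n+M)/(N+M) − n/(N+M) = M/(N+M).
- Note: n/N − n/(N+M) = (n/N) × M/(N+M).
- Ratio, note to text: n/N, the complete-case responder rate.

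**Numbers (assumed).**

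| n/N, M | k | Note | Text |
|---|---|---|---|
| 166/277, 3 | 0 | 166/277 = 59.93% | 169/280 = 60.36% |
| 166/277, 3 | 3 | 166/280 = 59.29% | 166/280 = 59.29% |
| 160/266, 14 | 0 | 160/266 = 60.15% | 174/280 = 62.14% |
| 160/266, 14 | 7 | 160/273 = 58.61% | 167/280 = 59.64% |
| 160/266, 14 | 14 | 160/280 = 57.14% | 160/280 = 57.14% |
| 265/266, 14 | 0 | 265/266 = 99.62% | 279/280 = 99.64% |
| 265/266, 14 | 7 | 265/273 = 97.07% | 272/280 = 97.14% |
| 265/266, 14 | 14 | 265/280 = 94.64% | 265/280 = 94.64% |

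In the middle example the span is 60.15 − 57.14 = 3.01 points under the note and 62.14 − 57.14 = 5.00 under the text. The ratio is 0.60, which is 160/266.

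**Range.** The row +0 shortfall is M(N−n)/[N(N+M)]. With N+M = 280 and M from 1 to 28, it runs from 0.02 to 0.52 points at about 95% responders, 0.07 to 1.98 at about 80%, and 0.18 to 5.00 at about 50%.

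**The case against.** **The mismatch is inferred.** The note does not say that nothing else is added, and no section writes the formula or says outright that the remaining M−k sites become responders. That is true, and it is why the formula needs to be stated. But no text adds imputed responders to n or to N, and the row labels count non-responders only, so a programmer working from the shell would naturally code n/(N+k). Nor can N already hold the missing sites, because adding the imputed non-responders would then count them twice.

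**The best case matters little for a persistence claim.** The worst-case row is correct, the note never flatters a product's own rate, and the SAP's tipping-point analysis for log counts also moves only in the unfavourable direction. This stands as a reason to rate the point minor. It does not remove the point, because both documents start the sequence at 0/M.

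**M may be very small.** Subjects stay at the facility until the 6-hour sample (Protocol 6.1). Counts can still be lost through laboratory error or loss to follow-up (SAP 6.4), three uncountable plates (SAP 6.1.1), or discontinuation, after which efficacy data are no longer collected (Protocol 6.3.1 and 7.2). SAP Table 4 also removes contaminated or undosed plates and pooled samples from the mITT counts, and the SAP does not say whether those sites belong to M. So M is unknown, and zero is possible.

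**A stronger reading.** A reader might infer that, because the shortfall is larger in an arm with a lower rate, the table exaggerates the advantage of the IP over saline. The documents do not support taking the point that far. Responder rates are summarised separately for each product, success is judged against the site's own baseline, and neither Table A.3.3 nor Table A.5.5 has a between-product contrast. Any such figure would also need assumed rates and assumed missingness in both arms.

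**Conclusion.** The point holds as a minor inconsistency that takes effect only if at least one 6-hour count is missing. On its natural reading, the Table A.5.5 note omits M−k missing sites in every row before +M, makes row +0 a copy of the complete-case rate, and shows n/N of the span that the text implies. Row +M is correct. When every observed site responds, row +0 is 100% under both rules and nothing is lost there.

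The size depends on values that the documents do not give. At about 60% responders, row +0 is low by about 0.4 points with 3 of 280 sites missing and by 2.0 points with 14 missing. In an arm near 100% the difference is negligible.

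The 6-hour rate sits under the FDA primary objectives, so a reader might infer that the FDA conclusion is at risk. It is not: the rate has no acceptance criterion and no test, and type I error, power and the success rules are unchanged.

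**What to change.** In SAP 6.4.1 and Table A.5.5, define row k, for k = 0 to M, as (n+M−k)/(N+M) for IP, AC and NC on each anatomical site. Replace the table note with: *All M sites with a missing 6-hour count are in the denominator; k are counted as non-responders and M−k as responders.* Change the column header from Subjects to Sites to match. Each subject receives two different products, one per side (Protocol 3.3.1), so within one product and body location the two counts should coincide; the header change is for consistency.

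The cost is a sentence in SAP 6.4.1, one table note, one header and one line of code. Protocol 13.4 already agrees with the formula, so no protocol amendment is needed. No new data are required.
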